15.4.3. Primary Specimen Biopsy Population

The primary specimen biopsy population includes all tissue samples where collection of biopsies from the primary specimen is performed in accordance with the primary specimen biopsy collection algorithm (Table 12.1). The Point-level Population will be used for the exploratory analyses.

15.4.4. Timepoints of Efficacy Analyses

15.4.4.1. Fluorescence Assessment at the End of SoC

Efficacy endpoints that evaluate diagnostic performance of PD G 506 A at the "initial fluorescence assessment at end of SoC" include fluorescence assessments of the *outside surface(s)* of the last resected *SoC-driven cavity shave specimens* (or the *outside surface* of the *primary specimen* if no cavity shave specimens are obtained) and fluorescence assessments of the *final cavity after SoC*.

Histopathology assessments for presence or absence of carcinoma are obtained from the *outside surface(s)* of the last resected *SoC driven cavity specimen(s)* removed (or the *outside surface* of the *primary specimen* if no cavity shave specimens are obtained) and the *inside surface(s)* of the first (innermost) *FL-driven cavity shave specimen(s)*, if collected (Figure 15.1).

SBI-CIP 20-002	Rev: v1.8	A prospective multi-center clinical study evaluating the use of PD G 506 A and the Eagle V1.2 Imaging System for the visualization of carcinoma during breast conserving surgery	Page: 100 of 157
-----------------------	--------------	--	------------------

[figure not shown]

Figure 15.1. Orientations Included in "Initial Fluorescence Assessment at the End of SoC" Endpoints and Analyses

15.4.4.2. Fluorescence Assessment During Fluorescence Guided Resection (FGR)

Efficacy endpoints that evaluate diagnostic performance of PD G 506 A "after SoC" include fluorescence assessments of the *outside surface(s)* of the last resected *SoC-driven cavity shave specimens* (or the *outside surface* of the *primary specimen* if no cavity shave specimens are obtained) fluorescence assessments of the *inside surface(s)* and *outside surface(s)* of all *FL-guided cavity shave specimens*, and fluorescence assessment of the *final cavity* after FGR. Histopathology assessments for presence or absence of carcinoma are obtained from the *outside surface(s)* of the last resected *FL-guided cavity shave specimen(s) removed (Error! Reference source not found.)*.

[figure not shown]

Figure 15.2. Orientations Included in "Fluorescence Assessment during Fluorescence Guided Resection (FGR)" Endpoints and Analyses

SBI-CIP 20-002 Rev: v1.8 A prospective multi-center clinical study evaluating the use of PD G 506 A and the Eagle V1.2 Imaging System for the visualization of carcinoma during breast conserving surgery	Page: 101 of 157
---	------------------

Completion of FGR and BCS SurgeryEfficacy endpoints that evaluate the diagnostic performance of PD G 506 A at the "completion of FGR and BCS surgery" include fluorescence assessment of the *final cavity* and the *outside surface(s)* of the last resected *FL-driven cavity* shave specimens, the *outside surface(s)* of the last resected *SoC-driven cavity shave specimens* (if no *FL-driven cavity shave specimens* are taken for the particular orientation), and the *outside surface(s)* of the *primary specimen* (if no cavity shave specimens are obtained for the particular orientation) (Figure 15.2). Histopathology assessments for presence or absence of carcinoma are obtained from the *outside surface(s)* of the last resected *specimen(s)* removed.

[figure not shown]

Figure 15.2: Orientations Included in "Completion of FGR and BCS" Endpoints and Analyses

15.4.4.3. Entire Resection

Efficacy endpoints that evaluate diagnostic performance of PD G 506 A over the entire resection, incorporate fluorescence assessments of all *specimen surfaces* and the *final cavity*. Histopathology assessments for presence or absence of carcinoma are obtained from the *outside surface(s)* of the *primary specimen*, and both inside and outside surfaces of *cavity shave specimens* (Figure 15.3).

[figure not shown]

Figure 15.3. Orientations Included in "Entire Resection" Endpoints and Analyses

15.5. Formulas

Detailed formulas for the primary, secondary, and exploratory endpoints can be found in Section 7.

15.6. Primary and Key Secondary Endpoint Analyses

There is one primary endpoint and three co-key secondary endpoints for this study: P(1.1), P(2.1), P(2.2) and P(2.3) See Section 7 for the formulas used. These four endpoints will each be tested at the 0.05 level. Only the primary efficacy endpoint test must be significant for the study to be considered positive. Information on the analyses and hypotheses are provided below.

15.6.1. Primary Endpoint:

1. P(1.1): Conversion Rate Among All Patients

The primary endpoint, P(1.1), is the percentage of participants with negative-margins following FGR among all patients following SoC. Participants that are converted from margin-positive after SoC to margin-negative after FGR will be considered a 'clinical success' and will be counted towards the numerator of the primary endpoint. If at the completion of Eagle V1.2 Imaging System assessment red PpIX FL is still observed on the *final margins after FGR* and/or in the *surgical cavity* and no further resection is performed, the anatomical surface(s) of residual fluorescence (i.e., S, M, P, L, I, A) and the reason for not performing further *FGR* is recorded. In such cases, orientation(s) involving FL observed in the *final margin after FGR* and/or in the *surgical cavity* will *not* contribute to the determination of a histopathologically-negative final margin for this primary endpoint.

Participants that are margin-positive after SoC and remain margin-positive after FGR will be considered a 'clinical failure' and will be counted towards the denominator of the primary endpoint proportion. See Section 7.1 for the formula.

The number and percentage of patients with negative-margins following FGR among patients with positive margins following SoC will be provided along with a two-sided 95% confidence interval calculated using the Wilson (score) method. The analysis will be performed using the mITT population.

The statistical hypothesis is as follows: H_0 : $P(1.1) \le 1\%$ vs $H_a = P(1.1) > 1\%$

If the lower bound of the Wilson (score) confidence interval is above 1%, the endpoint will be assumed to be statistically significant. The result is expected to be >3%.

SBI-CIP 20-002 Rev: v1.8 A prospective multi-center clinical study evaluating the use of PD G 506 A and the Eagle V1.2 Imaging System for the visualization of carcinoma during breast conserving surgery Page: 103 of 1	5 7
---	------------

15.6.2. Key Secondary Endpoints:

The secondary endpoints will be tested sequentially at the 0.05 level.

2. P(2.1) Conversion Rate among SoC margin-positive patients

The secondary endpoint, P(2.1), is the percentage of participants with negative-margins following FGR among patients with positive margins following SoC. Participants that are converted from margin-positive after SoC to margin-negative after FGR will be considered a 'clinical success' and will be counted towards the numerator and the denominator of this secondary endpoint. If at the completion of Eagle V1.2 Imaging System assessment, red PpIX FL is still observed on the *final margins after FGR* and/or in the *surgical cavity* and no further resection is performed, the anatomical surface(s) of residual fluorescence (i.e., S, M, P, L, I, A) and the reason for not performing further *FGR* is recorded. In such cases, orientation(s) involving FL observed in the *final margin after FGR* and/or in the *surgical cavity* will *not* contribute to the determination of a histopathologically-negative final margin for this primary endpoint.

Participants who are margin-positive after SoC and remain margin-positive after FGR will be considered a 'clinical failure' and will be counted towards the denominator of the primary endpoint proportion. See Section 7.1 for the formula.

The number and percentage of patients with negative-margins following FGR among patients with positive margins following SoC will be provided along with a two-sided 95% confidence interval calculated using the Wilson (score) method. The analysis will be performed using the mITT population.

The statistical hypothesis is as follows: H_o : $P(2.1) \le 3\%$ vs $H_a = P(2.1) > 3\%$. If the lower bound of the Wilson (score) confidence interval is above 3%, the endpoint will be assumed to be statistically significant. The result is expected to be >15%.

3. P(2.2): Patient-level Specificity

P(2.2) will be calculated on a patient-level using the mITT Population.

P(2.2) will be calculated as follows: Specificity = 100% x (TN_{patient} / (TN_{patient} + FP_{patient}))

The patient-level specificity estimate along with a two-sided 95% confidence interval calculated using the Wilson (score) method will be provided.

The statistical hypothesis is as follows: H_0 : $P(2.2) \le 70\%$ vs H_a : P(2.2) > 70%

SBI-CIP 20-002 Rev: v1.8 A prospective multi-center clinical study evaluating the use of PD G 506 A and the Eagle V1.2 Imaging System for the visualization of carcinoma during breast conserving surgery	Page: 104 of 157
---	------------------

If the lower bound of the confidence interval is above 70%, the endpoint will be assumed to be statistically significant. The patient-level specificity is expected to be >80%.

4. P(2.3): Patient-level Sensitivity

P(2.3) will be calculated on a patient-level using the mITT Population.

P(2.3) will be calculated as follows: Sensitivity = $100\% \times (TP_{patient} / (TP_{patient} + FN_{patient}))$

The patient-level sensitivity estimate along with a two-sided 95% confidence interval calculated using the Wilson (score) method will be provided.

The statistical hypothesis is as follows: H_0 : $P(2.3) \le 50\%$ vs H_a : P(2.3) > 50%

If the lower bound of the confidence interval is above 50%, the endpoint will be assumed to be statistically significant. The patient-level sensitivity is expected to be >70%.

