15.1. General Considerations

Descriptive summaries of variables will be provided where appropriate. For continuous variables, the number of non-missing values (n) and the median, mean, standard deviation, minimum, and maximum will be tabulated. For categorical variables, the counts and proportions of each value will be tabulated. Confidence intervals will also be provided as appropriate. All statistical tests will be performed at the 0.05 level.

Further details on all analyses will be provided in the statistical analysis plan (SAP).

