15.2. Sample Size Estimation

The sample size of Part A has been chosen on pragmatic grounds to be approximately 75 study patients. The number of patients ultimately included in Part A will be decided by the Steering Committee and the Sponsor based on the perceived understanding of the protocol by clinical sites and the feedback obtained during the Part A training phase. Part A will not be randomized; all study patients in Part A will receive PD G 506 A. Data acquired from Part A will be used to confirm the Investigators' understanding of fluorescence guided resection (FGR) procedures in the protocol and to confirm the sample size for Part B. Only data from participants in Part B will be used for the analyses of primary and secondary efficacy. Data from all patients in both Part A and Part B will be used for the evaluation of safety and analyses will include assessments of data from Part A and Part B separately, as well as all study patients (Part A and Part B together).

P(1.1) Conversion Rate among all patients =

patients with at least one histopathology-positive margin following SoC and histopathology negative final margins after FGR

All patients imaged (Arm 2)

SBI-CIP 20-002 Rev: v1.8 A prospective multi-center clinical study evaluating the use of PD G 506 A and the Eagle V1.2 Imaging System for the visualization of carcinoma during breast conserving surgery	Page: 96 of 157
---	-----------------

The sample size in Part B of the study is only driven by the primary endpoint P(1.1). The primary endpoint is intended to determine the percentage of patients with at least one histopathology-positive margin after SoC who then have all histopathology-negative margins after FGR (conversion rate among all patients in Arm 2). To demonstrate benefit, the point estimate P(1.1) must be statistically significantly greater than 1%. By meeting this primary endpoint, we will demonstrate that FGR adds clinical benefit above and beyond what is achieved with SoC.

Based on the expected 3% conversion rate estimate for P(1.1), a total of 500 patients will be required in Part B of the study to demonstrate statistical significance at a Type 1 error level of 0.05 with 90% power using a 2-sided Z test for a binomial proportion assuming a null hypothesis proportion of 1%.

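### Sections 15.6 and 15.6.2 do not gate the three key secondary tests on P(1.1) or stop at a failure, so those claims lack family-wise error control as written

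*Combined protocol and SAP*

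**What the plan says.** Section 15.6 sets out the family: "There is one primary endpoint and three co-key secondary endpoints for this study". The co-key label covers only the three secondaries; P(1.1) is a separate, single primary. The level follows: "These four endpoints will each be tested at the 0.05 level". So does the study success rule: "Only the primary efficacy endpoint test must be significant for the study to be considered positive".

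Section 15.6.2 opens with a different description for the secondaries: "The secondary endpoints will be tested sequentially at the 0.05 level". The endpoints are numbered 1 to 4 across 15.6.1 and 15.6.2, in the order P(1.1), P(2.1), P(2.2), P(2.3).

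Each endpoint then has a stand-alone rule. For the primary: "If the lower bound of the Wilson (score) confidence interval is above 1%, the endpoint will be assumed to be statistically significant". The rules for P(2.1), P(2.2) and P(2.3) have the same form, with nulls of 3%, 70% and 50%. None refers to the result of an earlier test. Section 15.1 adds only "All statistical tests will be performed at the 0.05 level" and leaves further detail to the SAP. The text reviewed contains no other multiplicity rule.

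**The concern.** Three things needed for a fixed sequence are not stated: that the secondaries are tested only if P(1.1) is significant, that testing stops at the first non-significant result, and that the numbering is the test order. Without them, 15.6 can be applied as four free-standing tests and 15.6.2 as a hierarchy. The two give different answers whenever an earlier test fails.

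This matters because P(2.1) to P(2.3) are not descriptive. They carry formal nulls and significance rules, and the Amendment 8 summary in Section 2 says they were set on FDA recommendation. If the choice between the two readings is left until results are known, it can be made to suit the data.

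**Working it through.** **1. The plan's own sample size (Section 15.2).** Inputs: null 1%, expected 3%, two-sided 0.05, 90% power, one-sample Z test. Using the null variance for the critical value:

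n = [(1.960 × √(0.01 × 0.99) + 1.282 × √(0.03 × 0.97)) / 0.02]² = [(0.1950 + 0.2186) / 0.02]² ≈ 427.7, so 428 in Arm 2.

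At 1:6 the total is 427.7 × 7/6 ≈ 499, against 500 stated, and 500 × 1.05 = 525. The figures reproduce, and they depend on P(1.1) only.

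**2. Effective level per test.** Requiring the lower bound of a two-sided 95% interval to exceed the null is a nominal one-sided 2.5% test.

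**3. Error over the three key secondaries, all three nulls true.**

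| Rule | One-sided 2.5% per test | Bonferroni bound |
|---|---|---|
| Three ungated tests, independent | 1 − 0.975³ = 7.3% | 3 × 2.5% = 7.5% |
| Fixed sequence gated on P(1.1) | at most 2.5% | – |

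If 0.05 is taken literally as the error of each test, the ungated figures are 1 − 0.95³ = 14.3% (bound 15%), against 5% for the sequence.

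**4. Where the readings part.** Wilson lower bound, with p = x/n and z = 1.960:

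L = [p + z²/(2n) − z√(p(1 − p)/n + z²/(4n²))] / (1 + z²/n)

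Primary, n = 428:
- 8/428: L = 0.95%, below 1%, fails.
- 9/428: L = 1.11%, passes.

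Nine is also the smallest passing count at n = 407 (428 less 5%) and n = 450 (525 × 6/7).

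P(2.1) has the same numerator as P(1.1) (Sections 7.1 and 7.2.1), but its denominator is the SoC-positive patients. The plan does not give that number. Assumption: the expected 3% for P(1.1) and 15% for P(2.1) imply 3/15 = 20% SoC-positive, and 0.20 × 428 ≈ 86.

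| Conversions | SoC-positive | L for P(2.1) | Against the 3% null |
|---|---|---|---|
| 6 | 86 | 3.2% | passes |
| 7 | 86 | 4.0% | passes |
| 8 | 86 | 4.8% | passes |
| 8 | 64 | 6.5% | passes |
| 8 | 128 | 3.2% | passes |

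So with 86 SoC-positive patients, 6 to 8 conversions fail the primary and pass P(2.1). With 8 conversions this holds from 64 to 128 SoC-positive patients (15% to 30% of 428).

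**5. How likely a failed primary is.** With a true rate of 3%, the exact binomial probability of 9 or more of 428 is 89.6%, so P(1.1) fails about 10.4% of the time even if the planning assumption is right.

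**The case against.** The best defence is that the two sentences are compatible. A fixed sequence also tests every endpoint at the full 0.05, so 15.6 may state only the level and 15.6.2 the procedure. On an ungated reading the word *sequentially* would have no function, and the running numbers 1 to 4 suggest an order. This largely stands as evidence of intent: a fixed sequence was probably meant. It does not supply the gate or the stopping rule, and the stand-alone success rules work against it.

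Second, detail is deferred to the SAP. A rule may be written there, so the finding is that the text reviewed lacks one, not that none will exist. A later SAP rule would still have to be reconciled with 15.6.

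Third, once P(1.1) has passed with at least 9 conversions, P(2.1) passes automatically unless 160 or more of 428 (37%) are SoC-positive: 9/159 has L = 3.01% and 9/160 has L = 2.99%. The remaining family is then mainly P(2.2) and P(2.3), with 1 − 0.975² = 4.9%. That is fair, but 4.9% is one-sided and compares with 2.5%, not with a two-sided 5%. It also presupposes the gate that is missing.

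A reader might go further and multiply over all four tests, 1 − 0.975⁴ = 9.6%. The documents do not support that as this trial's error rate. P(1.1) equals P(2.1) times the SoC-positive rate, so both can sit at their nulls only if 1/3 = 33% are SoC-positive. At the implied 20%, P(2.1) = 3% means P(1.1) = 0.6%, and the chance of 9 or more of 428 is then 0.13%, not 2.5%.

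**Conclusion.** The point holds, confined to the key secondary claims. As written, they have no family-wise control: about 7.3% nominal one-sided for three ungated tests, at most 7.5%, against 2.5% under a gated fixed sequence. The 7.3% assumes that all three nulls are true and that the tests are independent. The endpoints share patients, so it is an illustration and the Bonferroni bound is the safer statement. The 2.5% per test is itself nominal, because the Wilson rule is discrete: the exact one-sided error is 3.0% for P(1.1) at 428 and about 4.5% for P(2.1) at 86. The worked example assumes 428 analysed patients and about 86 SoC-positive.

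A reader might infer that the trial's overall type I error is inflated. It is not: no key secondary can rescue a failed primary, because Section 15.6 rests study success on P(1.1) alone. Nor are all four endpoints co-key. This is a contradiction to settle before unblinding, not a flaw in the primary analysis or the sample size.

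**What to change.** Replace the level sentence in 15.6 and the opening sentence of 15.6.2 with one rule. P(1.1) is tested first. Only if it is significant are P(2.1), P(2.2) and P(2.3) tested, in that order, each at the same level by the Wilson rule already given. Testing stops at the first non-significant result, and later endpoints are reported descriptively with their intervals. Delete the co-key label, and carry the same rule into the SAP.

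Cost: one paragraph in each document. No patients are added, because P(1.1) alone drives the sample size. The downside is that a later key secondary cannot be claimed after an earlier failure. If the sponsor prefers another order for the three, it should be fixed before unblinding.

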7.1. Primary Objective and Endpoint

Primary	Primary Endpoint					
Objective	Parameter Description	Parameter Formula		Abbreviated Description		
1.To evaluate the efficacy of PD G 506 A by demonstrating the clinical usefulness of PDG 506A to identify additional malignant breast tissue during BCS after SoC	Percentage of patients with at least one histopathology-positive margin following SoC who then have ALL histopathologynegative margins following FGR, among all patients imaged.	P(1.1) Conversion Rate = # patients with at least one histopathology-positive margin following SoC and histopathology negative final margins after FGR All patients imaged (Arm 2)	x 100%	Conversion rate among all patients		

	SBI-CIP 20-002	Rev: v1.8	A prospective multi-center clinical study evaluating the use of PD G 506 A and the Eagle V1.2 Imaging System for the visualization of carcinoma during breast conserving surgery	Page: 28 of 157
--	-----------------------	--------------	--	-----------------

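### Section 15.6.1 reports the primary conversion rate P(1.1) and its Wilson interval over the wrong denominator: patients margin-positive after SoC instead of all imaged Arm 2 patients

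*Combined protocol and SAP*

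**What the plan says.** Most of the plan defines P(1.1) over all patients.

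- Section 7.1 gives the formula, with the denominator "All patients imaged (Arm 2".
- Section 15.2 sizes the trial on the "conversion rate among all patients in Arm 2".
- Section 15.5 says "Detailed formulas for the primary, secondary, and exploratory endpoints can be found in Section 7", and the opening of Section 15.6 says "See Section 7 for the formulas used".
- Section 15.6.1 is headed as the conversion rate among all patients. Its opening sentence says that P(1.1) "is the percentage of participants with negative-margins following FGR among all patients following SoC".

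The next paragraph of 15.6.1 says that patients who are margin-positive after SoC and stay positive after FGR "will be counted towards the denominator of the primary endpoint proportion", and adds "See Section 7.1 for the formula". It does not mention patients who were already margin-negative after SoC.

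Then comes the sentence that sets out the reported result and attaches the two-sided 95% Wilson interval: "The number and percentage of patients with negative-margins following FGR among patients with positive margins following SoC will be provided". The success rule that follows compares the lower Wilson bound with 1% and names no denominator.

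**The concern.** The quoted sentence describes P(2.1), not P(1.1). Section 7.2.1 defines P(2.1) over patients with positive final margins after SoC, and Section 15.6.2 uses the identical sentence for it. Text seems to have moved in both directions, because the P(2.1) paragraph in turn calls P(2.1) the primary endpoint and cites Section 7.1.

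The location makes this more than untidy wording. Section 15.6 makes P(1.1) the only test that must be significant for a positive study. The 1% rule is applied to a Wilson interval, and this is the only sentence in 15.6.1 that says how that interval is formed. If it were followed, P(1.1) would become the same proportion as P(2.1), tested against 1% instead of 3%, and the 1%/3%/428 design would no longer apply to it. Section 15.1 defers details to a separate SAP, so the error could be carried forward.

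**Working it through.** **Inputs.** Null 1%, expected 3%, two-sided 0.05, 90% power (15.2); Arm 2 N = 428 and Arm 1 N = 72 (15.2); success if the Wilson lower bound exceeds 1% (15.6.1); P(2.1) expected above 15% (15.6.2). The share of patients margin-positive after SoC in this trial is not stated in Section 15.

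**1. Reproduce the plan's N.** For a one-sample Z test with the null variance under H0:

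n = [1.960·√(0.01·0.99) + 1.282·√(0.03·0.97)]² / (0.03 − 0.01)² = 427.7, so 428.

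Section 15.2 does not state which variance was used. The alternative variance throughout would give 764.4. The exact match with the null variance shows that 428 was sized for the proportion over all Arm 2 patients. Also 428/6 = 71.3, so 72, and 428 + 72 = 500.

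**2. Decision rule with the intended denominator (n = 428).** The Wilson lower bound is

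[p + z²/2n − z·√(p(1−p)/n + z²/4n²)] / (1 + z²/n), with z = 1.960.

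- 9/428 = 2.10%: lower bound 1.11%, passes.
- 8/428 = 1.87%: lower bound 0.95%, fails.

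Nine conversions are needed. The exact binomial P(X ≥ 9) is 0.030 at 1% and 0.896 at 3%, in line with the planned 90% power.

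**3. Decision rule with the literal denominator.** The smallest number of conversions with a lower bound above 1% is:

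| SoC-positive patients | Conversions needed |
|---|---|
| 18–55 | 2 |
| 56–102 | 3 |
| 103–156 | 4 |

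**4. Illustration.** Take the expected 3% and 15% as point values (an assumption, since the plan says above 15%). Conversions: 0.03 × 428 = 12.8, about 13. SoC-positive patients: 12.84/0.15 = 85.6, about 86.

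| | Intended | Literal |
|---|---|---|
| Estimate with 13 conversions | 13/428 = 3.0% | 13/86 = 15.1% |
| Wilson lower bound | 1.78% | 9.05% |
| Conversions needed to pass the 1% rule | 9 | 3 |

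Under the literal reading 3/86 passes (lower bound 1.19%) and 2/86 does not (0.64%). Three conversions are 3/428 = 0.70% of all patients, below the 1% null.

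**5. Conditional error.** Suppose the literal sentence overrode Section 7 and the true all-patients rate were exactly 1%. Let s be the SoC-positive share, M ~ Bin(428, s) and X given M ~ Bin(M, 0.01/s), with the threshold set by M. The values of s are assumed.

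| s | 10% | 15% | 20% | 25% | 30% |
|---|---|---|---|---|---|
| Chance of passing | 92.7% | 82.4% | 79.9% | 68.3% | 62.1% |

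These are not the plan's error rates. With the intended denominator the corresponding figure is 3.0%.

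**The case against.** The strongest reply is that this is a copying slip that the document itself resolves. The heading, the opening sentence, the hypothesis line stated for P(1.1), Sections 7.1, 15.2 and 15.5, and the sample size all point to all patients. A reader would have to override all of them to apply the sentence literally. That stands, and it is why the point is an error of wording and not an open choice of estimand.

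A second reply is that the 62% to 93% figures mix two hypotheses: a literal denominator with a null defined over all patients. Against its own null (1% among SoC-positive patients), the literal rule passes 6.7%, 3.7%, 5.4%, 4.1% and 4.1% of the time at shares of 10% to 30%. This is also correct. The literal reading tests a different and easier hypothesis, and the large figures only show what that would mean for the all-patients claim the trial is meant to support.

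Third, the opening sentence also describes the percentage, and saying that SoC-positive failures count in the denominator does not exclude anyone else. Both are fair. But the quoted sentence is still the only one that attaches the Wilson method, and the deciding rule depends on that interval. No clause says that Section 7 prevails over Section 15 if they conflict.

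The opening sentence also leaves out that converted patients must first be margin-positive, although the sentence after it supplies this. The differing mITT descriptions in 15.2 and 15.4.1 are a separate matter.

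**Conclusion.** The concern holds. The sentence in 15.6.1 that sets out the primary estimate and its interval names the P(2.1) denominator and contradicts the formula that the section itself cites. The intended denominator is clear, and the sample size is unaffected because it reproduces on that basis.

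The case for correcting it is that the text is wrong in the one analysis that decides the trial. It does not rest on the conditional error rates, which need both a literal application and an assumed SoC-positive share. On the 3%/15% illustration, the literal rule would cut the bar from 9 conversions to 3. A correction made now raises no question; one made after data are available could look like a choice of denominator.

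**What to change.** In 15.6.1, replace the sentence so that it reports the number and percentage of patients who were margin-positive after SoC and have all margins negative after FGR, with all imaged Arm 2 patients as the denominator, together with the two-sided 95% Wilson interval. In the preceding paragraph, state that patients who were margin-negative after SoC also count in the denominator, as the 7.1 formula requires.

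It would be sensible in the same edit to correct the P(2.1) paragraph in 15.6.2, which calls P(2.1) the primary endpoint and cites 7.1, where 7.2.1 holds its formula.

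The cost is two sentences in 15.6.1, plus the optional tidying in 15.6.2. Data collection, patients, sample size and the 1% threshold do not change, because the new wording restates Section 7.1. The change should be made before the text is carried into the SAP.

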Using a randomization ratio of 1:6 (Arm 1-SoC; Arm 2: PD G 506 A), a total sample size of 525 patients (Arm 1: N=72; Arm 2: N=428) would be required, accounting for a 5% loss to follow-up. The primary efficacy analysis will be based on the mITT (modified intention-to-treat population), which includes all Part B patients randomized to Arm 2 who undergo surgery and have recorded surgical histopathology data.

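### The Wilson lower-bound rule has an exact one-sided error of 3.0–3.9% for P(1.1) at 428–450 patients, above the 2.5% the design implies; for P(2.1) it is about 4.5% if some 86 patients are margin-positive

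*Combined protocol and SAP*

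**What the plan says.** Section 15.6.1 tests P(1.1), the conversion rate among all imaged Arm 2 patients, against a null of at most 1% with a one-directional alternative. The rule is: "If the lower bound of the Wilson (score) confidence interval is above 1%, the endpoint will be assumed to be statistically significant". The interval is a two-sided 95% Wilson interval. This one test decides whether the study is positive.

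Section 15.6.2 handles P(2.1), the conversion rate among patients with positive margins after SoC, against 3% in the same way: "If the lower bound of the Wilson (score) confidence interval is above 3%, the endpoint will be assumed to be statistically significant". For this endpoint the plan anticipates a rate above 15%.

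Section 15.2 sets the sample size: "Based on the expected 3% conversion rate estimate for P(1.1), a total of 500 patients will be required in Part B", the aim being "to demonstrate statistical significance at a Type 1 error level of 0.05 with 90% power using a 2-sided Z test for a binomial proportion" with a 1% null. At 1:6 allocation this becomes "a total sample size of 525 patients (Arm 1: N=72; Arm 2: N=428) would be required, accounting for a 5% loss to follow-up".

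This text gives no exact test, no continuity correction and no check of the rule's actual error. It also gives no number for the denominator of P(2.1). Section 15.1 leaves further analysis detail to the SAP, but the decision rule itself is explicit.

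**The concern.** The Wilson bound rests on a normal approximation to the binomial. Under a 1% null with 428 patients, only 428 × 0.01 = 4.28 conversions are expected, so the approximation is rough in the upper tail, and that is the only tail that can produce a success.

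If the rule admits more false successes than 2.5%, the pivotal claim is slightly easier to reach than the design implies. A borderline result would also depend on the interval method: 9 conversions in 428 give a Wilson lower bound of 1.11% (success) and an exact lower bound of 0.97% (failure). Nine is not remote when 428 × 0.03 = 12.8 conversions are expected under the planning assumption. A choice of method made after such a result would not be credible.

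**Working it through.** **Inputs.** Section 15.2: null 1%, expected 3%, two-sided 0.05, power 90%, Arm 2 = 428, total 525, ratio 1:6, 5% loss. Section 15.6: Wilson 95% intervals, nulls of 1% and 3%, P(2.1) expected above 15%.

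**1. Reproduce the plan's N.** One-sample Z test with null variance:

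n = [(1.960·√(0.01×0.99) + 1.2816·√(0.03×0.97)) / 0.02]² = [(0.1950 + 0.2186) / 0.02]² = 427.7, so 428.

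428 × 7/6 = 499.3, about 500, and 500 × 1.05 = 525. The same formula with one-sided 0.05 gives 365; using the sample variance gives 764 (two-sided) or 623 (one-sided). Only two-sided 0.05 with null variance fits, so the upper tail carries 2.5%.

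**2. Convert the P(1.1) rule into a count.** The Wilson lower bound exceeds p₀ exactly when x > n·p₀ + 1.960·√(n·p₀·(1−p₀)).
- n = 428: 4.28 + 1.960 × √4.237 = 8.31, so at least 9.
- n = 450 (525 × 6/7, no loss): 4.50 + 1.960 × √4.455 = 8.64, so at least 9.

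The count is 9 for every n from 428 to 450.

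**3. Exact binomial operating characteristics for P(1.1).**

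| n | Rule | One-sided error at 1% | Power at 3% |
|---|---|---|---|
| 428 | Wilson, ≥ 9 | 3.02% | 89.6% |
| 450 | Wilson, ≥ 9 | 3.94% | 92.4% |
| 428 | Exact, ≥ 10 | 1.21% | 82.7% |
| 450 | Exact, ≥ 10 | 1.66% | 86.9% |

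Between 428 and 450 the Wilson error rises steadily and is above 2.5% throughout. A two-sided reading also counts 0 conversions, where the Wilson upper bound lies below 1%. That adds 1.35% at 428 and 1.09% at 450, for totals of 4.4% and 5.0%.

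The error moves in steps. At n = 406 the rule is at least 8, with error 5.39%; at n = 407 it is at least 9, with error 2.29%. From 400 to 450, only 407 to 413 hold 2.5%.

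**4. P(2.1), on an assumed denominator.** If 3% of all patients convert and 15% of margin-positive patients convert, then 3%/15% = 20% are margin-positive, and 0.20 × 428 = 86. The threshold is 2.58 + 1.960 × √(86×0.03×0.97) = 5.68, so at least 6.
- Wilson, ≥ 6: error at 3% is 4.49%; power at 15% is 99.3%.
- Exact, ≥ 7: error 1.50%; power 98.0%.

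Over denominators of 60 to 110 the Wilson error runs from 2.2% (at 93) to 6.5% (at 72). It exceeds 2.5% for 46 of the 51 values; the exceptions are 73, 74 and 93 to 95. Averaged over a Binomial(428, 0.20) denominator it is 3.9%.

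**The case against.** The plan never writes 2.5%. It writes 0.05 and a two-sided test, and total two-sided size at 428 is 4.4%, inside 0.05. This stands as far as it goes: a reader might infer that the plan breaches a level it states, and at the planned evaluable size it does not. The 2.5% is an inference from the two-sided interval, the one-directional alternative and the reproduction of N. It remains the relevant figure because 0 conversions can never be declared a success, so that tail does not offset false successes in the other.

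A reader might also infer that the sample size or the 90% power is wrong. The documents do not support that. N reproduces, exact power under the plan's own rule is 89.6%, and the Wilson bound inverts the same null-variance Z test used for N, so design and analysis agree.

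The excess at 428 is about half a point and reflects ordinary discreteness. A mid-P calculation for 9 of 428 gives 2.1%, so another accepted criterion would pass the same cut-off. The 3.9% needs 450 evaluable patients, meaning no loss; Section 11.1 replaces participants who leave before Week 2, so sizes towards 450 are possible but are not the planning case. All of this stands, and it argues against insisting on an exact test for P(1.1).

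Finally, the 4.5% for P(2.1) rests on a denominator the documents do not give, and P(2.1) does not decide the trial. Both are correct; the figure must carry its assumption and range.

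**Conclusion.** The point holds in a limited form. For P(1.1), the rule's exact false-success rate is 3.0% at 428 evaluable and 3.9% at 450, above the implied 2.5% at every size between. This rests on reading 0.05 as two-sided, which the plan's own N requires.

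For P(2.1), the error is 4.5% at an assumed 86 margin-positive patients, with a range of 2.2% to 6.5% over 60 to 110. It is above 2.5% for most denominators in that range, but not for all.

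Two stronger conclusions do not follow: that Wilson intervals are invalid here, and that an exact test is required for the primary endpoint. The excess is moderate. What is missing is a statement of the rule's real operating characteristics, and it is worth supplying because this single rule decides the study.

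**What to change.** **P(2.1).** Decide on the exact (Clopper-Pearson) lower bound and keep the Wilson interval for display. At 86 patients this means at least 7 conversions instead of 6, with error 1.5% and power at 15% of 98.0% instead of 99.3%. The cost is SAP wording and about 1 point of power at the assumed denominator.

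**P(1.1).** Before unblinding, commit to one of two options.
- Keep Wilson. State the critical count (9 for 428 to 450 evaluable) and the actual one-sided error (3.0% to 3.9% over that range) in place of the nominal level, and recompute both if the final number falls outside it. The cost is a slightly less favourable stated error.
- Adopt the exact bound. At least 10 conversions are then needed, and power should be restated as about 83% at 428 or 87% at 450. This is conservative (error 1.2% to 1.7%) and gives up the 90% target at the planned N. Exact 90% power is first reached at 471 in Arm 2, which is 471 − 428 = 43 more patients, and holds at every size only from 511.

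The choice for P(1.1) is the sponsor's. Neither option needs more patients unless the exact bound is adopted and the 90% target is kept.
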